5.3.4.2 Treatment-Emergent Adverse Events

An adverse event (AE) will be classified as 'treatment-emergent' if the onset date/time was after the start date/time of study treatment and on or before 30 days after last dose of study treatment. Where dates or times are missing or partially missing, AEs will be assumed to be treatment-emergent, unless there is clear evidence (through comparison of partial dates/times, see [Section 7.3.1](#)) to suggest that the AE started prior to dosing.

AEs will be classified into the following study phases based on the onset date/time of the AE after any imputations:

- Pre-Treatment Phase: All AEs with onset date/time prior to the first dose of study treatment
- Treatment Phase: All AEs with onset date/time at the time of or after the first dose of study treatment (Day 1) up to and including the date of the last dose of treatment received
- Follow-up Phase: All AEs with onset date after the date of the last dose of treatment received

For participants who complete 36 weeks of dosing per protocol, the Treatment Phase will be from Day 1 to the Week 36 visit, and the Follow-up Phase will start after the Treatment Phase and last until their last day in the study. In all cases the day will be assumed to start at 00:00 hours and end at 23:59 hours. Adverse events occurring in both the Treatment Phase and Follow-up Phase are classified as treatment emergent.

For participants who were administered active treatment in the parent study, the Parent Treatment Phase will be defined from the first dose of IMP in the parent study up to the Day 1 in this study.

The onset phase of all AEs will be included in the relevant data listings.

6 Sample Size

The sample size of the study will be determined by the number of participants who enrol from qualifying atopic dermatitis parent studies with EDP1815.

7 General Considerations

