2. STUDY OBJECTIVE(S)

2.1. Primary Objectives

The primary study objective is to evaluate the long-term safety and tolerability of EDP1815 in the treatment of atopic dermatitis. The primary endpoints to measure this objective will be the incidence and rate per 100 patient-years of treatment-emergent adverse events during the 36-week treatment period and the 4-week follow-up period of this study, and during the treatment period of this study and the relevant parent study.

TEAEs will be defined as all events starting after first dose of study drug and on or before 28 days after last dose for each participant. All TEAEs will be included in the assessments of incidences and rates, regardless of compliance with study medication, use of other medications or deviations from the study protocol.

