9.4. Reporting and Recording AEs

The Investigator will carefully monitor each participant throughout the study for possible AEs. In order to confirm complete safety data collection, all AEs occurring during the study (i.e., after the signing of the Informed Consent form) must be reported in the CRF. AEs reported during the parent study that are ongoing at the end of treatment visit will continue to be followed up during EDP1815-208 until resolution or the participants completes the study, whichever is first.

All AEs will be collected and reported in the electronic data capture (EDC) system and compiled into reports for periodic reviewing by the Medical Monitor. The Medical Monitor shall promptly review all information relevant to the safety of the investigational product, including all serious adverse events (SAEs). Special attention will be paid to those that result in permanent discontinuation of the investigational product being studied, whether serious or non-serious.

If the investigator learns of any SAE, including a death, at any time after a participant has been discharged from the study, and he/she considers the event to be reasonably related to the IMP or study participation, the investigator must immediately notify the sponsor (or designee).

Serious AEs that occur more than 30 days after the last dose of IMP need not be reported unless the investigator considers them related to the IMP.

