9.4.2. Assessment of Severity

The severity, or intensity, of an AE refers to the extent to which an AE affects the participant's daily activities or their health. The intensity of the AE will be rated in accordance with the CTCAE Version 5.0. Adverse events related to temperature and abnormal laboratory results that are not found in the CTCAE Version 5.0 will be rated in accordance with the FDA Guidance for Industry *Toxicity Grading Scale for Healthy Adult and Adolescent Volunteers Enrolled in Preventive Vaccine Clinical Trials* [Appendix [14.4 Toxicity Grading Scale](#)].

Changes in the severity of an AE should be documented to allow an assessment of the duration of the event at each level of intensity to be performed. Adverse events characterized as intermittent do not require documentation of onset and duration of each episode.

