9.2.1 Estimands

The primary safety estimands will use the FAS or the parent study specific FAS for the study/cohort specific analysis.

Treatment condition: actual treatment received will be considered.

Population summary measure of interest:

- For the endpoints looking at the period defined by this study only - the incidence and rate per 100 patient-years of each category of TEAEs (DPS1)
- For the endpoints looking at the period defined since first dose of the active IMP in this study and the relevant parent study - the rate per 100 patient-years of each category of TEAEs by treatment group (DPS2)

Intercurrent events will be accounted for in the following manner:

Table 1: Intercurrent Event Strategies of the Primary Estimand

Discontinuation of treatment	The use of prohibited medications or TCS/TCI rescue therapy, non-compliance with study drug, and any deviations from protocol
Composite strategy Only events which start within 30 days after discontinuation of treatment (TEAEs) will be included in the assessments of incidences and rates	Treatment policy strategy: Data will be used as collected

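### Treatment-emergent AEs are defined by onset only, so an AE that began before the first active dose and worsens on EDP1815 is in neither primary period if the worsening stays in the existing record

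*SAP*

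**What the plan says.** Protocol 2.1 sets the rule by the start of the event: "TEAEs will be defined as all events starting after first dose of study drug and on or before 28 days after last dose". SAP 5.3.4.2 keeps that basis with a longer window: an AE is treatment-emergent "if the onset date/time was after the start date/time of study treatment and on or before 30 days after last dose". SAP Table 9 declares the move from 28 to 30 days and leaves the onset basis alone.

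SAP 5.3.4.2 also assigns phases by onset. One of them reads "Pre-Treatment Phase: All AEs with onset date/time prior to the first dose of study treatment". The parent-study phase exists for some participants only: "For participants who were administered active treatment in the parent study, the Parent Treatment Phase will be defined from the first dose of IMP".

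The primary estimand applies the rule. Table 1 in SAP 9.2.1 says "Only events which start within 30 days after discontinuation of treatment (TEAEs) will be included in the assessments of incidences and rates". SAP 11.3 admits only treatment-emergent AEs (TEAEs) to the summaries and leaves pre-treatment AEs to the listings.

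Two protocol provisions show that worsening of an earlier AE was foreseen. Section 9.4 states: "AEs reported during the parent study that are ongoing at the end of treatment visit will continue to be followed up during EDP1815-208". Section 9.4.2 states: "Changes in the severity of an AE should be documented to allow an assessment of the duration of the event at each level". Section 9.4.4 leaves the details of completing the AE form to eCRF guidelines that are not part of these documents.

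**The concern.** The primary endpoint is the incidence and rate of TEAEs, and all 12 categories in SAP 9.2 are subsets of TEAEs. The onset rule therefore decides what each of them can contain.

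In an extension study, participants arrive with AEs already open. Those who had placebo in 207 meet EDP1815 for the first time in 208; they form three of the seven dose-history groups in Protocol 11.3.2. If one of them has a mild AE that began on placebo and it becomes severe or serious on EDP1815, that change belongs to the safety question the study asks. A rule that looks only at the first onset date may never count it.

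**Working it through.** The plan states no figure on this point, so the check applies the rule to constructed cases.

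**Inputs.** Rule: first dose < onset ≤ last dose + 30 days (SAP 5.3.4.2). The reference dose is the first 208 dose for the 208-only period (DPS1) and the first active dose in 207 or 208 for the combined period (DPS2). Assumed days, with the first 208 dose as day 1: first 207 dose on day −112 (16 weeks × 7, Protocol 4.1), last 208 dose on day 252 (36 × 7), worsening on day 60. The window closes on day 252 + 30 = 282. In every case except the last, the onset date is known and the worsening stays in the existing record.

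| Case | Onset day | DPS1: 1 < onset ≤ 282? | DPS2 reference day | In DPS2? |
|---|---|---|---|---|
| Parent placebo, began during 207 | −40 | No | 1 | No |
| Parent placebo, began between 208 consent and first dose | −1 | No | 1 | No |
| Parent active, began before first 207 dose | −120 | No | −112 | No |
| Parent active, began on active drug in 207 | −40 | No | −112 | Yes, by onset |
| New AE in 208 | 60 | Yes | 1 | Yes |

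With the protocol's 28-day window (closing on day 252 + 28 = 280) the results are the same.

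The first three cases are in neither period. The third also assumes that 207 recorded AEs before its first dose; 208 does so from consent (Protocol 4.5, footnote p), but the 207 protocol is not available. The fourth case is counted in DPS2 because of its onset, and DPS1 misses its worsening.

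**If worsening opens a new dated record.** The new record has onset day 60 and passes both tests, so all five cases are counted in both periods. The loss depends wholly on the record convention.

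**What the documents say about that convention.**
- Protocol 9.4.1 lists one CTCAE grade and one onset and resolution per event, and 9.4.2 wants a duration at each intensity. Together these can be read as one dated entry per grade.
- Protocol 9.4.2 can equally be read as one event with several intensity levels. Protocol 9.5.5 distinguishes new AEs from changes in existing ones, which leans towards one record.
- No passage settles it.

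**Early-stop package.** SAP 9.1 and 11.1 restrict safety reporting to the 208 period, and Table 9 records that the study was terminated early. In SAP 16.3.1, 4 of the 14 DPS1 AE tables are kept (14.3.1.1.1, 14.3.1.2.1, 14.3.1.5.1 and 14.3.1.14.1) and 0 of the 14 DPS2 tables. The fourth case is then in no summary table either. That follows from the declared 208-only scope together with the onset rule.

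**The case against.** The strongest reply is that no loss is shown. It exists under one record convention and vanishes under the other, and the deciding guidelines are not available. One grade per event, with a duration wanted at each level, can fairly be read as pointing to separate dated entries. This stands as a limit on the claim. A reader might infer that the plan certainly undercounts its primary endpoint; the documents do not support that.

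A second reply is that worsening is already captured elsewhere, and in part it is. Protocol 9.1 and 9.4.1 make a clinically significant worsening of atopic dermatitis recordable as an AE. Protocol 9.3 lets a worsened pre-existing condition qualify as one, but its context is a condition in the medical history, and it does not clearly reach an AE already on record. For unknown dates SAP 5.3.4.2 is conservative: "Where dates or times are missing or partially missing, AEs will be assumed to be treatment-emergent, unless there is clear evidence". That does not help when the onset is known to precede the dose.

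A third reply is that DPS1 and DPS2 hold all observed data, and that early-stop data are shown without exclusions (SAP 9.1). The reported categories are still TEAEs, so the definition still filters them.

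Finally, the consequence is modest. Analyses are descriptive (Protocol 11.1 and 11.4). Expedited SAE reporting (Protocol 9.5) and the halting criteria (9.9) do not depend on TEAE status. A reader might infer a gap in participant protection; there is none on this ground.

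**Conclusion.** The point holds conditionally. The onset-only rule is explicit in both documents, and no provision makes worsening treatment-emergent. If a worsening stays in the existing record and the onset date is known, an AE that began before the first active dose and rises in grade or becomes serious on EDP1815 is in neither primary period and appears only in the AE listing. The clearest example is one that began on placebo in 207. An AE that began on active drug in 207 is missed by DPS1 only, and hence by every early-stop summary table.

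The number of affected events cannot be derived: the documents give no frequency of open AEs at entry or of their worsening. The cases above show where the rule reaches, and counting them would not measure how much is lost. This merits correction because a stated rule can undercount the primary safety endpoint and the remedy is cheap. The effect is on descriptive reporting only.

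**What to change.** In SAP 5.3.4.2, with an entry in Table 9 (the route already used for the 30-day window):

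- Define a TEAE as an AE with onset after the reference dose, or an AE present before it whose CTCAE grade increases or which becomes serious after it, in either case within 30 days after last dose. Count each such AE once per period.
- Set the reference dose as the first 208 dose for DPS1 and the first active dose for DPS2.
- State whether a grade increase stays in the existing record or opens a new one. If it opens a new one, count only the new record, so that no worsening is counted twice; the clause then changes nothing.
- Show onset-only counts alongside.
- List worsenings without a date separately. The existing presumption concerns missing AE dates. Extending it to undated worsenings of AEs with a known pre-dose onset would be a new rule, and it would sit badly with the early-stop instruction not to impute (SAP 9.1 and 11.1).

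The cost is one definition, one Table 9 entry and one derivation. AE records must be linked between 207 and 208, although SAP 7.4.2 already brings parent-study data into all analyses and Protocol 9.4.2 already asks for severity changes. Some worsening dates will be missing, partly because intermittent AEs need no dates for each episode. TEAE counts can only stay the same or rise, and the onset-only display will show by how much.

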7.1 Analysis Populations

7.1.1 Participant Analysis Populations

7.1.1.1 Enrolled Population

The enrolled set will consist of all participants who sign the ICF.

7.1.1.2 Full Analysis Population

The full analysis population will consist of all participants who receive any IMP.

7.1.1.3 Other Populations

Other parent study specific analysis sets may also be used in interim analyses which will be defined by the subset of participants from the FAS who were previously enrolled from the specific parent studies or study cohorts. Such populations will be named xxxxxx Full Analysis Set, where xxxxxx stands for the study specific subset identifier.

7.1.2 Defined Data Point Sets

7.1.2.1 Data Point Set 1 (DPS1)

DPS1 consists of all observed data collected following the first dose of IMP in this study until 30 days after the last dose of IMP.

Note, baseline data will be taken from the parent study.

7.1.2.2 Data Point Set 2 (DPS2)

DPS2 consists of all observed data collected following the first dose of active IMP, either in the parent study or in this study until 30 days after the last dose of IMP in this study.

7.1.2.3 Data Point Set 3 (DPS3)

DPS3 consists of all observed data collected at a scheduled visit in this study.

Note, changes from baseline will be derived using baseline data from the parent study.

7.1.2.4 Data Point Set 4 (DPS4)

DPS4 consists of all observed data collected at a scheduled visits in this study or the parent study for participants who enter this study.

7.1.2.5 Data Point Set 4a (DPS4a)

DPS4a is a subset of DPS4, excluding any data collected within 4 weeks after the use of permitted rescue medications for atopic dermatitis or at any time after the use of prohibited medications for atopic dermatitis.

7.1.2.6 Data Point Set 4b (DPS4b)

DPS4b is a subset of DPS4 for responder endpoints only, where data collected within 4 weeks after the use of permitted rescue medications for atopic dermatitis, at any time after the use of prohibited medications for atopic dermatitis, or at scheduled endpoints after withdrawal from treatment due to treatment-failure related reasons (related AEs, lack of efficacy, requirement for alternate psoriasis therapy) will be replaced by 'non-responder'.

7.1.2.7 Data Point Set 5 (DPS5)

DPS5 consists of all observed data collected following the first dose of IMP in this study.

7.2 Covariates and Subgroups

No inferential statistical testing will be performed so no covariates will be defined.

7.3 Missing Data

Unless otherwise specified as part of the intercurrent event strategy, missing data will not be imputed. Imputation of missing efficacy data due to intercurrent events will be performed in DPS4a and DPS4b as described in [Section 7.1.2](#).

7.3.1 Partial Dates/Times

Partial dates and times for AEs, medical conditions and concomitant medications will be imputed for the purpose of assigning study phases and calculating duration. Listings will always include the reported date/time information rather than any imputations.

Partial AE onset and concomitant medication start dates will be imputed as follows:

- If only the month and year are specified, and the month and year of the start of treatment in 208 are not the same as the month and year of the start date, then use the 1st of the month.
- If only the month and year are specified, and the month and year of the start of treatment in 208 are the same as the month and year of the start date, then use the date of start of treatment. If this results in a start date after a known or partial end date, then use the 1st of the month.
- If only the year is specified, and the year of the start of treatment in 208 is not the same as the year of the start date, then use January 1 of the year of the start date.
- If only the year is specified, and the year of the start of treatment in 208 is the same as the year of the start date, then use the date of the start of treatment. If this results in a start date after a known or partial end date, then use January 1 of the year of the start date.
- If the start date is completely unknown, then use the date of the start of treatment in 208. If this results in a start date after a known or partial end date, do not impute the start date.

Partial AE onset start times will be imputed as follows:

- If the actual or imputed start date is the same as the 208 treatment start date, and the start time is completely missing, then use the time of start of treatment.
- If the actual or imputed start date is not the same as the 208 treatment start date, and the start time is completely missing, then use 00:00.
- If the actual or imputed start date is the same as the 208 treatment start date, and the start time is partially missing (hh:XX) then use the following:
 - If the hour is the same as the hour of the start of treatment time then use the complete time of the start of treatment (i.e., both hours and minutes)
 - If the hour is not the same as the hour of the start time then use hh:00.
- If the actual or imputed start date is not the same as the 208 treatment start date, and the start time is partially missing (hh:XX) then use hh:00.

Partial medical conditions start dates will be imputed as follows:

- If only the month and year are specified, then use the 1st day of the month.
- If only the year is specified, then use January 1st of that year.
- If the start date is completely unknown, do not impute the start date.

Partial AE resolution, medical condition stop dates and concomitant medication stop dates and date last smoked will be imputed as follows:

- If the event, condition or medication is flagged as ongoing, do not impute the stop date.
- If only the month and year are specified, then use the last day of the month.
- If only the year is specified, then use December 31 of that year.
- If the stop date is completely unknown, do not impute the stop date.

Partial AE resolution and concomitant medication stop times will be imputed as follows:

- If the actual or imputed stop date is non-missing, and the stop time is completely missing, then use 23:59 on that date.
- If the actual or imputed stop date is non-missing, and the stop time is partially missing, then hh:59 for missing minutes.
- If the actual or imputed stop date is missing, do not impute the stop time.

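### SAP 7.3.1 imputes partial AE and medication start dates against the 208 start only, which does not fit DPS2 for participants on active drug in 207 and can move 207 records into the 208-only period

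*SAP*

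**What the plan says.** SAP 7.3.1 has one set of start-date rules for AEs and concomitant medications. Partial dates "will be imputed for the purpose of assigning study phases and calculating duration". Every comparison is with the 208 start:

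- Month and year known, not the 208-start month: "start of treatment in 208 are not the same as the month and year of the start date, then use the 1st of the month".
- Month and year known, same month as the 208 start: "start of treatment in 208 are the same as the month and year of the start date, then use the date of start of treatment". An end-date guard follows: "If this results in a start date after a known or partial end date, then use the 1st of the month".
- Year only, not the 208-start year: "then use January 1 of the year of the start date". In the 208-start year, the 208 start is used, with the same kind of guard falling back to January 1.
- Nothing known: "If the start date is completely unknown, then use the date of the start of treatment in 208", with no imputation if an end date precedes it.

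The start-time rules use the same anchor: on any date other than the 208 start date, a missing time becomes 00:00.

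The data sets fed by these dates do not all start at 208. SAP 7.1.2.2 states: "DPS2 consists of all observed data collected following the first dose of active IMP, either in the parent study or in this study". SAP 4.2 makes the combined 207 and 208 period a primary endpoint, and SAP 7.4.2 brings parent data into all analyses. SAP 5.3.4.2 assigns AE phases from the onset after imputation, and SAP 5.3.3.10 assigns a rescue course to a period by its start day. SAP 5.3.4.2 also sets a default: "Where dates or times are missing or partially missing, AEs will be assumed to be treatment-emergent, unless there is clear evidence" of onset before dosing, with a cross-reference to 7.3.1.

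**The concern.** For a participant on active drug in 207, the DPS2 clock starts about 16 weeks before the date that 7.3.1 uses. Nothing in 7.3.1 refers to the first active 207 dose, and nothing ties a record to the study that collected it. Two kinds of misplacement follow.

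1. Early on-drug AEs in 207 can receive a date before the first active dose. On the imputed date they fall outside DPS2; on the 5.3.4.2 default they are TEAEs. Two programmers could reach different counts from the same SAP.
2. AEs and TCS/TCI courses that began in 207 can be dated to the first 208 dose. They can then enter the 208-only TEAE count (DPS1, first primary endpoint) or the 208-only rescue rate. For a participant on active drug in 207, a moved AE was already in DPS2 and stays there. For a participant on placebo in 207, DPS2 also starts at the 208 first dose, so a moved placebo-period AE could be counted as on active drug in both sets.

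**Working it through.** The documents give no figure for this point, so there is none to reproduce. The check applies the rules to dates.

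**Worked example.** First active 207 dose 15 March 2022; 208 start 112 days (16 weeks) later, 5 July 2022.

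| Recorded start (true onset) | End date | Imputed start | Result |
|---|---|---|---|
| Mar 2022 (20 Mar) | none | 1 Mar | before first active dose |
| May 2022 (10 May) | none | 1 May | correctly placed |
| Jul 2022 (2 Jul) | none | 5 Jul | moved to 208 |
| Jul 2022 (2 Jul) | 3 Jul | 1 Jul | guard works, not moved |
| 2022 (10 Apr) | none | 5 Jul | moved to 208 |
| 2022 (10 Apr) | 20 Apr | 1 Jan | before first active dose |
| unknown (10 Apr) | none | 5 Jul | moved to 208 |
| unknown (10 Apr) | 20 Apr | not imputed | no start date |

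**Average over calendar dates.** Assumptions, none of them in the documents: first active 207 dose equally likely on each day of a 365-day year; 208 start 112 days later; true onsets uniform over those 112 days; 207 dates not already imputed under the parent plan; end date either absent or 7 days after onset.

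For month-only records with no end date the result can be derived by hand. In a month of n days, the onset days that fall in the first-dose month and are set before dosing, summed over all dosing days except the 1st, come to n(n−1)/2. Over the year:

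7 × 465 + 4 × 435 + 378 = 5,373

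5,373 / 365 = 14.72 days on average, and 14.72 / 112 = 13.1%.

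The same sum gives the days of the 208-start month that precede the 208 start, so 13.1% are moved. Applying all the rules day by day gives:

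| Partial start | End date | Before first active dose | Moved to 208 start | Kept in parent period | Not imputed |
|---|---|---|---|---|---|
| Month and year | none | 13.1% | 13.1% | 73.7% | 0.0% |
| Month and year | onset + 7 days | 13.1% | 5.4% | 81.4% | 0.0% |
| Year only | none | 15.5% | 84.5% | 0.0% | 0.0% |
| Year only | onset + 7 days | 80.2% | 6.2% | 13.6% | 0.0% |
| Unknown | none | 0.0% | 100.0% | 0.0% | 0.0% |
| Unknown | onset + 7 days | 0.0% | 6.2% | 0.0% | 93.8% |

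A 7-day gap between the studies changes these by at most about one point (month-only, no end date: 14.72 / 119 = 12.4% each way).

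**Scale.** These are shares of partial-date records, not of all records. If 1% to 5% of parent-period AEs had month-only dates and no end date (an assumption), each misplacement would affect 0.131 × 1% = 0.13% to 0.131 × 5% = 0.66% of them, before the 5.3.4.2 default is applied.

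**With the anchor changed.** Setting month-only onsets against the first active dose gives 0% before dosing and 0% on or after the 208 start, under the same assumptions with no end date.

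**The case against.** The strongest reply is that other parts of the SAP already contain the problem.

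- *The treatment-emergent default.* A month-only date that matches the first-dose month is not clear evidence of onset before dosing, so 5.3.4.2 would keep the AE. This stands in part. It rules out calling the loss certain, but 5.3.4.2 sends the reader to 7.3.1 for the comparison and then assigns phases from imputed onsets. The conflict remains.
- *The definition of DPS1.* SAP 7.1.2.1 covers data collected after the first 208 dose, and SAP 11.3 limits that summary to AEs starting in this study. On a strict reading, a record collected in 207 never qualifies. But no rule assigns a record by its source study, AEs ongoing at the end of 207 treatment are followed in 208 so that the guard cannot act on them, and rescue courses go by start day.
- *The end-date guard.* It works where an event is known to have ended before 208, and the table shows by how much.
- *Participants on placebo in 207.* The 208 start is their correct DPS2 anchor, so they cannot lose DPS2 events. This stands.
- *Dates already imputed in 207.* The SAP does not say. If they were, much of the point falls away.

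Four stronger readings are tempting, and the documents do not support them:

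- A reader might infer that almost all early AEs are lost, since 1 − 12/365.25 = 96.7% of first doses do not fall on the 1st. That is a share of day-missing AEs in one month only, and the default may keep even those.
- A reader might infer that shifted rescue starts create false non-response at 208 Week 4. That effect comes mainly from the separate rule setting a month-only stop date to month end, which re-anchoring the start would not change.
- A reader might infer that an onset imputed to exactly the first-dose time is not treatment-emergent. The phase definitions in 5.3.4.2 include onset at the time of first dose, so this is wording only.
- A reader might infer that the early-stop results are distorted. SAP 9.1 and 11.1 allow no imputation there and report the 208 period only, and the appendix marks the DPS2 and rescue tables as not produced.

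**Conclusion.** The rule is wrong as written for the full planned analysis. SAP 7.3.1 uses one anchor for data sets that start at different times. AEs in the month of the first active 207 dose, or sent to January 1, can be lost from DPS2 because two SAP rules conflict. Records that began in 207 can enter the 208-only TEAE count or rescue rate when no end date precedes the 208 start. Month-only onsets in later parent months, before the 208-start month, are placed correctly.

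About 13% of month-only parent-period records without an end date are affected in each direction; year-only and unknown starts fare worse. This rests on the uniform-date assumptions above and on 207 dates arriving unimputed. The number of partial dates is unknown, so the overall effect is probably small, though systematic. The study is descriptive, so no test is at stake.

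The study was terminated early (SAP 14), and the reduced outputs are untouched. That reading takes 9.1, 11.1 and the Early Stop column as governing; the introductory line of SAP 16.3, which says early-stop safety outputs follow the original plan, should be reconciled with them.

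**What to change.** In SAP 7.3.1:

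1. Impute start dates and times against the first active dose (207 or 208) for DPS2, and against the first 208 dose for DPS1.
2. Do not impute a start on or after the 208 first dose for any AE or medication first collected in 207.
3. State that the 5.3.4.2 default prevails whenever the partial date is compatible with onset after the relevant first dose, subject to item 2 for records first collected in 207.
4. State whether 207 dates arrive already imputed under the parent plan.

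As a wording change only, align the TEAE sentence in 5.3.4.2 with the phase definitions by using on or after in place of after.

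The cost is a few sentences in the SAP and a small change to the date-imputation macro. No new data are needed, and the reduced early-stop outputs do not have to be rerun.
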